## 2.0 BACKGROUND AND RATIONALE

### 2.1 Background

Oral mucositis is a significant and common toxicity experienced by patients who receive high-dose chemotherapy as a preparatory regimen for a hematopoietic cell transplant (HCT). Furthermore, oral mucositis has been reported as the single most debilitating side effect reported by patients undergoing transplantation.[1] The incidence of HCT conditioning mucositis is estimated to range between 76% and 89%; however, comparisons are difficult due to variability in patient ages, treatments and criteria for scoring oral mucositis.[2, 3]

Oral mucositis is a progressive process that begins shortly after the administration of high-dose chemotherapy and results from DNA strand breaks that result in direct cellular injury of cells in the basal epithelium and within the submucosa resulting in mucosal destruction.[2] Additionally, mucositis represents local tissue reactions including damage from reactive oxygen species, inflammatory cytokines, and damage to submucosa connective tissues and vasculature. Stages of oral mucositis include mucosal burning, erythema, edema with progression to ulceration. Ulceration occurs most commonly on the nonkeratinized mucosa of the mouth floor, tongue, buccal mucosa and soft palate.[3] Oral mucositis is noted several days after completion of chemotherapy with a peak in severity between 6 and 12 days post-transplant.[4]

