Oral ulcerations are painful, may become secondarily infected, bleed and impact nutritional intake. Together these factors increase the need for parenteral nutrition, opioid administration for pain and predispose the patient to secondary infection and bacteremia. The cost of oral mucositis can be excessive due to increased utilization of antibiotics, blood products, pain medication and supplemental nutrition thus leading to longer hospitalizations. According to Sonis et al.,[5] a one point increase in peak mucositis grade in HCT has been associated with a 2.1 fold increase in risk of significant infection, 2.7 additional days of parenteral nutrition, 2.6 additional days of hospitalization, additional hospital cost of \$25,405 and 3.9 fold increase in risk of mortality with the first 100 days. While reporting benefit, the literature is limited in describing the efficacy of treatment for oral mucositis prevention and treatment among pediatric patients. Most studies have reviewed the efficacy of adult HCT oral mucositis interventions, with the inclusion of laser therapy recommended in adult oral mucositis guidelines.[2] Currently there is insufficient evidence for the application of PBM inclusion into oral mucositis guideline in the pediatric oncology population.[6]

This is a nurse led innovation utilizing a novel therapy for the prevention and treatment of the single most debilitating side effect reported in patients undergoing HCT. This innovative proposal has the potential to change our established Nursing Standard of Oral Care Guidelines for children and

adolescents undergoing a HCT through planned and coordinated application of daily PBM with standard oral care. If the PBM is found to reduce the severity and duration of oral mucositis, the change in nursing routine with the inclusion of nurse delivered PBM will have a direct impact on improving health outcomes specifically patient reported pain, decrease in positive blood and oral cultures and less days of nutritional support. A decrease in the severity and duration of oral mucositis will also have a potential impact on health care cost with a decrease in supportive care measures, which may subsequently decrease days of hospitalization.

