### ***HCT Patient Experience at St. Jude***

To better understand our patient experience, we conducted a retrospective review of the HCT patient experience and reviewed the medical records of 45 patients. [21] Patients were divided into two groups based on mucositis severity (mucositis defined as  $\geq$  grade 3 on the Common Terminology Criteria of Adverse Events). Demographic and clinical data were obtained via electronic medical record review and compared between groups.

This retrospective study reviewed transplant admissions between June 2015 and May 2016.[21] During this period, 75% of the allogenic transplant patients had  $\geq$  grade 3 mucositis with median mucositis onset at Day 3 (range -3 to 9) after progenitor cell infusion, median mucositis duration of 11 days, median of 9 days from (range 3 to 26) mucositis onset to engraftment and a median of 2 days (range -21 to 26) from engraftment to the end of mucositis. All of the 25 patients received parenteral nutrition and 96% received pain medications for oral pain. Patients with  $\geq$  grade 3 mucositis were more likely than those with grade 1/2 mucositis to have positive blood or oral cultures ( $p=0.018$ ), to have undergone an allogeneic transplant [ 17 of 21 patients ( $p=0.008$ )] and had significantly longer hospitalizations ( $p=0.002$ ). However, our review did find a subset of patients receiving auto transplant, such as neuroblastoma, to be at risk for high grade mucositis.

Our retrospective data revealed the onset of mucositis can be as early as Day -3 with continuation until engraftment. While studies have variability in timing of PBM, these findings support our proposed initiation of therapy to begin on the first morning of conditioning until engraftment with an ANC  $\geq 500$  for two consecutive days. Seventy-five percent of the those with grade 3 mucositis had undergone an allogenic transplant and 33% autologous. Therefore, patients undergoing autologous transplant and at risk for grade 3 mucositis, as identified by the bone marrow transplant clinicians will be included in the exploratory objective.

To determine sample size, we extended our review of allogenic transplant recipients from May 2015 to June 2019. Our review identified 93 first allogeneic transplant patients, with 66 (71%) developing grade 3 mucositis during transplant.

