#### 10.2.2 Statistical analysis for the secondary objective

*To compare clinical manifestations associated with the development of oral mucositis between those treated with daily PBM and a matched control. Clinical factors to include: mucositis grade, duration, and days to engraftment.*

*Hypothesis 2: Children and adolescents treated with extra-oral PBM will develop lower grade mucositis, with shorter mucositis duration (days) than the comparison matched control.*

Patients enrolled in the PBM study will be matched to a transplant control that did not receive PBM by age, sex, primary disease and transplant regimen. For a patient receiving PBM, the patients with the same sex, primary disease and transplant regime will be used as the candidate pool. The patient in the pool with the smallest difference of age is selected as matching. If there is more than one patient in the pool that satisfies the smallest difference of age, a reproducible random number generator will be used to randomly select one patient out of the multiple candidates.

The patient identifier, age, sex, primary disease and transplant regime for the patients without PBM in the historical data will be sent to the Biostatisticians without the outcome of development of grade 3 mucositis. The patient identifier for the selected patients in the historical data will be determined. Then other information for these patients will be obtained for analysis.

The two groups will be compared from day 1 of conditioning regimen until engraftment (2 consecutive days of an ANC>500) or Day+20.

The PBM group and the historical group without PBM will be compared on mucositis grade, duration of mucositis (number of days) and days from cell infusion to engraftment. We will compute the descriptive statistics (mean, standard deviation, median, and range) of the duration of mucositis and days to engraftment. We will also compute the descriptive statistics (count and percentage) of mucositis grade. To compare the clinical variables between the PBB and matched control groups, we will use generalized linear model with the variables for matching as covariates. The difference will be assessed by two-sided Wald tests with type I error rate  $< 0.05$ . For the duration of mucositis, the subset of patients who developed Grade 3 mucositis will be compared with their match control patients with similar methods described above.

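### The duration comparison in 10.2.2 stops at engraftment or Day +20, although about half or more of the institution's own reviewed episodes outlast engraftment and Hypothesis 2 states no window

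*Combined protocol and SAP*

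**What the plan says.** Hypothesis 2 (Sections 1.2 and 10.2.2) predicts lower-grade mucositis and fewer days of it than in matched controls, with no end date. Hypothesis 1 (Section 1.1), by contrast, does carry a window.

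The analysis text of 10.2.2 sets the window: "The two groups will be compared from day 1 of conditioning regimen until engraftment" or Day +20. The outcomes compared include "duration of mucositis (number of days) and days from cell infusion to engraftment". Duration is also compared in a subgroup: "the subset of patients who developed Grade 3 mucositis will be compared with their match control patients".

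Section 4.1 lists duration among the matched-comparison variables and makes the cut-off whichever of the two events comes first. It also ends observation of allogeneic patients there, and Section 6.3 takes patients off study on the last day of PBM. Nothing says how to treat mucositis still present at the cut-off.

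The institutional review in Section 2.2 (HCT Patient Experience at St. Jude) puts the typical onset at Day 3. For the length of episodes it gives "median mucositis duration of 11 days, median of 9 days from (range 3 to 26) mucositis onset to engraftment". How far mucositis persisted past that point is reported as a separate figure, namely "a median of 2 days (range -21 to 26) from engraftment to the end of mucositis". The same section supports the treatment window by saying that "the onset of mucositis can be as early as Day -3 with continuation until engraftment".

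**The concern.** An episode that outlasts engraftment has its length replaced by the time from onset to engraftment. If PBM speeds healing after that point, the endpoint cannot show it. The timing makes this likely to matter: Section 2.1 describes mucositis "with a peak in severity between 6 and 12 days post-transplant", and the institutional medians put engraftment near Day +12.

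The cut-off is also an outcome that the same section compares. Matching and adjustment use age, sex, primary disease and transplant regimen, and the controls are historical, so nothing secures equal engraftment or onset timing. Earlier engraftment in PBM patients, or later onset with unchanged duration, would look like a benefit. Later engraftment would mask a real one.

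The result has an intended use. Section 2.1 begins its case for changing nursing care with "If the PBM is found to reduce the severity and duration of oral mucositis".

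**Working it through.** **1. Consistency of the institution's figures (Section 2.2).** Onset to engraftment 9 days + engraftment to end of mucositis 2 days = 11 days, which matches the stated median duration. Medians need not add, so this is only a consistency check.

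**2. Illustration from the medians.** Onset Day 3; engraftment Day 3 + 9 = 12; end Day 3 + 11 = 14. The window records 9 of 11 days and loses 2/11 = 18%. In such a patient a 2-day shortening shows as 0 and a 3-day shortening as 1.

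**3. Share affected.** A median end 2 days after engraftment means that at least about half of the reviewed episodes were still present after engraftment. This needs no model.

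**4. Model for size.** The documents give no standard deviations, so the spreads are assumptions. Let O be onset day, G days from onset to engraftment and D duration.
- O: normal, mean 3, SD 2.5, clipped to the printed range of −3 to 9.
- G: lognormal, median 9, log-SD 0.5 or 0.6. D: lognormal, median 11, log-SD 0.55 or 0.8. Correlation of G and D: 0 or 0.5.
- Window count = min(D, G, 20 − O). Fixed count = min(D, 20 − O).
- 66 per group, 10,000 runs, unadjusted two-sided 5% Wald test on days, zeros included. Matching and covariates are not modelled.

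Narrower spreads do not fit the printed ranges. In samples of 25 or 45 with zero correlation, log-SD 0.35 for G reaches the 26-day maximum in only 3–5% of samples, against 34–84% at 0.5–0.6.

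The mean of D is 11·exp(σ²/2): 12.8 days at σ = 0.55 and 15.1 at 0.8. A 20% shortening is therefore about 2.6 or 3.0 days.

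**5. Results.** In this model 60–67% of episodes are cut at the window. If 30–50% of episodes are milder (assumed median 5 days), the share is 40–52%.

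| Scenario | Window | Fixed Day +20 |
|---|---|---|
| Pure 20% shortening: share of it seen | 20–29% | 44–66% |
| Pure 20% shortening: power | 0.12–0.27 | 0.31–0.61 |
| Duration unchanged, PBM engrafts 1 day earlier: rejection | 7–20% | 5–6% |
| Duration unchanged, PBM engrafts 2 days earlier: rejection | 17–61% | 5–6% |
| Duration unchanged, PBM onset 2 days later: rejection | 29–65% | 7–13% |
| Onset 2 days later, same end day: power | 0.74–0.94 | 0.58–0.75 |
| Prevention only (71% vs 51% affected): power | about 0.46–0.51 (lowest 0.43) | 0.47–0.54 |

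The rejection ranges also cover mixes in which not every patient has mucositis or some episodes are milder. Prevention uses the grade 3 rates of Section 10.1 as a stand-in for any mucositis. With milder episodes in the mix, the share of a 20% shortening seen is 26–45% (window) and 50–75% (fixed).

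If PBM shortens duration by 20% but PBM patients engraft 1 day later, the window shows only 6–12% of the shortening (11–33% with milder episodes). With equal timing and no effect it rejects 5–6%, so the level holds.

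**6. Would the engraftment comparison give warning?** Its power is about 0.12–0.22 for a 1-day difference and 0.35–0.64 for a 2-day difference, over raw and log scales.

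**7. Grade 3 subset.** 51% of 66 is about 34 per group. Power for a 20% shortening is 0.12–0.17 (window) against 0.36–0.37 (fixed) at duration log-SD 0.55, and 0.09–0.12 against 0.19–0.20 at 0.8. Matched controls are simplified here as all having mucositis.

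**The case against.** The best defence is that the plan does define its endpoint: a short hypothesis is made operational by a stated window that is the same in both groups. A count of mucositis days on treatment is legitimate. That stands, provided it is named as such. As written, it is called duration.

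A second objection is that a fixed Day +20 also truncates. That stands too. Under the assumed spreads 23–30% of episodes are still ongoing at Day +20 (12–23% with milder episodes), so Hypothesis 2 needs rewording in either case. The difference is that a fixed day does not move with engraftment.

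Third, the loss depends on how PBM works. If it only prevents mucositis, the two counts are nearly equal. If it only delays onset with the same end day, the present window is stronger. The large loss belongs to shortening of established episodes. At duration log-SD 0.8, power for that is weak with any window (0.28–0.29 even for full duration).

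A reader might infer that the planned comparison is biased. The documents do not support this: nothing in them indicates that engraftment or onset timing differs between PBM patients and controls, and the bias is conditional on such a difference. Nor would the engraftment comparison be useless as a warning. It usually misses a 1-day difference but catches a 2-day one about a third to two-thirds of the time.

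The institutional review is small: 45 records, including autologous patients, with an unclear denominator for the medians. It may describe mainly grade 3 or higher episodes, in which case it fits the Grade 3 subset best.

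**Conclusion.** The point holds for this secondary endpoint. The stated rule does not measure duration as Hypothesis 2 words it. For at least about half of the reviewed episodes it records onset-to-engraftment time, and it ties the count to an event that is not balanced by design. That much rests on the protocol's text and medians. The sizes rest on assumed spreads: for a pure 20% shortening, power is about 0.12–0.27 against 0.31–0.61 to a fixed Day +20.

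The median-patient illustration should not be read as saying that every 2-day shortening vanishes. Across the modelled population 20–29% of a 20% shortening is still seen. The primary monitoring rule in 10.1 is unaffected. The change is worth making, with moderate confidence in its size.

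**What to change.** For the duration endpoint, in PBM patients and matched controls alike, count days with mucositis from day 1 of conditioning to a fixed Day +20 regardless of engraftment. Use the routinely charted clinical grades that Section 6.2 already collects. Score patients without mucositis as zero. State one rule for death or discharge before Day +20 and apply it identically to both groups.

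Reword Hypothesis 2 (1.2 and 10.2.2) as days with mucositis to Day +20. Amend 4.1 (end of observation and of the matched comparison only), 6.3 and 10.2.2 together, with PBM delivery unchanged. Keep the present count as a supporting analysis named *mucositis days to engraftment or Day +20*. Report by group the onset day, days to engraftment and the share with mucositis ongoing at each cut-off.

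If charts cannot be extended, rename the endpoint, align Hypothesis 2 with it, and interpret it alongside onset day and days to engraftment.

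Cost: about a week more chart abstraction per patient in both groups (Day 20 − Day 12 = 8 days at the medians), with no extra visits, procedures or patients. Downsides: possible charting gaps after discharge; some remaining sensitivity to onset delay (7–13% rejection for a 2-day delay with unchanged duration); and lower power than the present window if PBM only delays onset. The institutional review shows that end-of-mucositis timing could be abstracted, not that daily grades exist throughout.

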**Table Summary of Photobiomodulation Therapy Delivered**

Case number	Days on protocol a	Days received treatment b	Total cumulative dose c (J/cm  )	Treatment site = right face	Treatment site = midline face	Treatment site = left face	Treatment site = left neck	Treatment site = midline neck	Treatment site = right neck

aDays on protocol defined as from the first day of hematopoietic cell transplantation conditioning through engraftment

bDays received treatment defined as days with treatment during any of the on-protocol days

cCummulative dose define as single treatment dose multiplied by the number of treatment sites (up to 6 in total) for each treatment session

Efficacy will be assessed with assessment of grade 3 mucositis development from day 1 of conditioning to Day +20 of transplant or engraftment as a binary outcome (yes/no)

[figure not shown]
Daily observation: The observation of oral mucositis will be conducted by non-study staff and conducted as clinical care by the nurse, advanced practice provider and/or physician.

Assessment: Each patient or parent proxy will complete the Children's Mucositis Assessment via ipad along with documentation of mucositis grade, duration, days of nutrition support, use of narcotics, positive oral and blood cultures.

Each patient will be matched and compared to a previously treated patient. The comparison will be matched on primary disease, conditioning regimen, age and sex, with comparison of treatment variables of mucositis grade, duration, pain medications, days of nutritional support, blood and oral cultures, to day +20 or engraftment (depending upon which occurs first).

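### Days to engraftment is analysed as a plain day count beside a Day +20 window, with no rule for patients who engraft later, die or never engraft

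*Combined protocol and SAP*

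**What the plan says.** Section 10.2.2 sets the comparison period for PBM patients and matched historical controls: "The two groups will be compared from day 1 of conditioning regimen until engraftment (2 consecutive days of an ANC>500) or Day+20". Section 4.1, describing the same matched comparison, confirms that the earlier event closes it: "to day +20 or engraftment (depending upon which occurs first".

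The next paragraph of 10.2.2 says the groups "will be compared on mucositis grade, duration of mucositis (number of days) and days from cell infusion to engraftment". The summaries are ordinary ones: "We will compute the descriptive statistics (mean, standard deviation, median, and range) of the duration of mucositis and days to engraftment". For the test, "we will use generalized linear model with the variables for matching as covariates", and "The difference will be assessed by two-sided Wald tests with type I error rate" below 0.05. No censoring, cumulative incidence or time-to-event method is named. Nothing says what value a patient receives who has not engrafted by Day +20, who dies first, or whose graft fails.

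Three other places bear on the point:

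- Section 6.3 takes patients off study on the last day of PBM, which for an allogeneic patient is Day +20 or engraftment.
- The chart abstraction list in section 6.2 includes time to engraftment, with no Day +20 limit.
- Section 2.2 (HCT Patient Experience at St. Jude) reports mucositis onset between Day -3 and Day 9, and a "median of 9 days from (range 3 to 26) mucositis onset to engraftment".

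**The concern.** Engraftment is both an endpoint and one of the two events that close the window. If the window applies to this endpoint, an engraftment date is seen only when it falls on or before Day +20. Scoring later patients as 20, or leaving them out, removes the slow tail of the distribution.

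Because the plan does not say which rule applies, capped values, engrafters by Day +20 only, and full chart times are all open, and the choice could be made after the data are seen. The two groups might also be treated differently: controls are historical and can have complete chart dates, while PBM patients go off study at Day +20.

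A separate gap does not depend on the window. A generalized linear model on days has no outcome to use for a patient who dies before engraftment or never engrafts.

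**Working it through.** The plan gives no sample size, power or effect size for this endpoint, so there is no stated figure to reproduce.

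**Step 1. Does engraftment after Day +20 occur in the sponsor's own series?**

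Engraftment day = onset day + days from onset to engraftment. In section 2.2 the earliest onset is Day -3, the latest is Day 9, and the longest interval is 26 days.

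- Earliest possible engraftment for the patient with the longest interval: -3 + 26 = Day +23.
- Latest possible: 9 + 26 = Day +35.

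So at least one patient engrafted after Day +20, provided the two ranges describe the same patients. The sum of the medians, 3 + 9 = Day +12, is only a rough guide to typical engraftment. It suggests that late engraftment is a tail, whose size the documents do not give.

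**Step 2. Effect of a cut at Day +20 in both groups**

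Assumptions, not document figures: normal engraftment times with mean μ and SD σ, and a true difference of 2 days (PBM mean = μ - 2). Let a = (20 - μ)/σ.

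- Capped mean: μΦ(a) - σφ(a) + 20[1 - Φ(a)]
- Mean with late engrafters dropped: μ - σφ(a)/Φ(a)

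Worked case, control μ = 12, σ = 5. For controls a = 1.6, Φ = 0.945, φ = 0.111; for PBM (mean 10) a = 2, Φ = 0.977, φ = 0.054.

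- Capped: 11.884 - 9.958 = 1.926 days, a loss of (2 - 1.926)/2, about 4%.
- Dropped: 11.413 - 9.724 = 1.689 days, a loss of about 16%.

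| Control mean, SD | Controls after Day +20 | Capped: days (loss) | Dropped: days (loss) |
|---|---|---|---|
| 12, 4 | 2.3% | 1.97 (1%) | 1.85 (8%) |
| 12, 5 | 5.5% | 1.93 (4%) | 1.69 (16%) |
| 16, 4 | 16% | 1.78 (11%) | 1.40 (30%) |
| 16, 5 | 21% | 1.68 (16%) | 1.26 (37%) |
| 18, 4 | 31% | 1.54 (23%) | 1.11 (44%) |
| 18, 5 | 35% | 1.45 (28%) | 1.03 (49%) |

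**Step 3. A more skewed shape**

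The second check was a simulation with lognormal times, 66 per group, 5-30% of controls after Day +20, control median Day 12 or 16, and a PBM median 15% shorter. Attenuation was about 2-64% if capped and 10-81% if dropped. Capping cost essentially no power. Dropping usually did: with 20% late and a median of Day 16, power fell from 0.93 to 0.76. With no true effect and the same rule in both groups, rejection stayed at about 5-6%.

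**Step 4. Only the PBM group is cut**

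With no true effect, the spurious difference is μ minus the capped or dropped mean. Over the same SDs it is 0.03-0.12 days (capped) or 0.22-0.59 days (dropped) at mean 12, and 0.33-1.15 or 1.15-2.81 days at means 16-18. It always makes PBM look faster.

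**The case against.** The strongest reply is that the plan never says engraftment dates stop at Day +20. The endpoint has its own start and end, "duration of mucositis (number of days) and days from cell infusion to engraftment", whereas the window starts on the first day of conditioning and may be meant for the mucositis measures. The list of windowed variables in section 4.1 does not include engraftment. Section 6.2 abstracts time to engraftment from the chart without a limit, and going off study does not bar chart review. The sponsor's earlier review evidently recorded engraftment beyond Day +20. All of this stands. A reader might infer that late engrafters will be lost; the documents do not establish that. They support only that the window sentence and the abstraction list point different ways.

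It is also fair that section 2.2 proves one late engrafter rather than a proportion. Its text moves between subsets, so that patient cannot be firmly assigned to the allogeneic group. The rough centre near Day +12 favours the small end of the table.

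The endpoint is minor. It appears in the objective as restated in 10.2.2, but not in section 1.2 or Hypothesis 2, and no hypothesis claims that PBM changes engraftment.

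The reply does not remove the gap for deaths and graft failures. Complete chart dates make a day count workable for patients who engraft, but give the others no value.

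**Conclusion.** The point holds as an unresolved conflict plus a missing rule. The window in 10.2.2 and the unlimited chart item in 6.2 need reconciling, because the sponsor's own figures show that engraftment can fall on Day +23 or later. Whichever is meant, patients who die or do not engraft are unaccounted for.

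The size is conditional. With both groups cut alike and normal times, a true 2-day difference loses about 1-16% if engraftment centres near Day 12, and 11-49% if it centres on Day 16-18; a heavier tail can cost more. The means, SDs and 2-day effect are assumptions.

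Two stronger readings are not supported. Bias towards no difference is not certain, since cutting only the PBM group reverses it. Nor is there an inflated false-positive rate when there is no true effect and both groups follow the same rule. The primary efficacy decision is unaffected. This should be corrected, but it is not critical.

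**What to change.** In section 10.2.2, state that the Day +20 limit does not apply to days to engraftment, and that the engraftment date is taken from the chart in the same way for PBM patients and controls. Replace the generalized linear model on days with a time-to-event analysis: cumulative incidence of engraftment with death or graft failure as competing events, and a Cox or Fine-Gray model with the matching variables as covariates.

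If follow-up for this endpoint must end at Day +20, censor there in both groups, or compare the proportions engrafted by Day +20.

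The cost is SAP wording and slightly more abstraction for patients who engraft late. The item is already on the section 6.2 list, and no new patients, visits or assessments are needed. The change concerns data capture and analysis only; it does not touch when PBM treatment stops.
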